1. STUDY SYNOPSIS AND OVERALL DESIGN

Study title

A phase 2, multicentre, randomized, double-blind, placebo-controlled study to assess the efficacy and safety of 400 mg twice a day oral ladarixin in patients with new-onset type 1 diabetes.

Study Number MEX0114 [EudraCT Number: 2014-003968-20]

Study period

Projected starting date (first-patient-in):	December 2015
Projected completion of patient accrual (last-patient-in):	December 2016
Projected study end date (last-patient-last-visit):	December 2017

Study design

The study will be a phase 2, multicentre, double-blind study. It will involve 72 patients with new-onset type 1 diabetes (T1D), randomly (2:1) assigned to receive either ladarixin treatment (400 mg b.i.d. for 3 cycles of 14 days on/14 days off – treatment group) or placebo (control group). The two groups will be balanced within each centre. Recruitment will be competitive among the study sites, until the planned number of patients is enrolled.

Sample size calculation has been based on the 2-hour area under the curve (AUC) of C-peptide response to a Mixed Meal Tolerance Test (MMTT) observed 12 months after randomization, as these are the only available data that best match the T1D population expected to be randomized in this trial (age, time from diagnosis, etc.) [Lachin, 2011]. On the other hand, the time frame for the primary endpoint (2-hour AUC of C-peptide response to the MMTT) has been set at week 13±1 in order to maximise the potential to observe an effect of ladarixin, considering the PK profile in humans as well as the reversibility of the pharmacological effect on CXCR1/2 receptors. Such an approach is appropriate for a phase 2 proof of concept trial. Follow-up is anyway extended up to 12 months.

Objectives/endpoints

The objective of this clinical trial is to investigate whether ladarixin has sufficient activity (preservation of β -cell function and slow-down of the progression of T1D) to warrant its further development (proof of concept trial). The safety of ladarixin in the specific clinical setting will be also evaluated.

Efficacy endpoints will be:

- 2-hour area under the curve (AUC) of C-peptide response to a Mixed Meal Tolerance Test (MMTT) [Primary endpoint. Time frame: baseline, week 13±1].
- 2-hour AUC of C-peptide response to the MMTT [Time frame: baseline, weeks 26±2 and 52±2].
- Average (previous 3 days) insulin requirements (IU/kg/day) [Time frame: baseline, weeks 13±1, 26±2 and 52±2].

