3. OVERALL STUDY DESIGN AND PLAN DESCRIPTION

3.1. STUDY DESIGN

The study will be a phase 2, multicentre, double-blind study. It has been designed to investigate (proof of concept) whether ladarixin has sufficient activity (preservation of β -cell function and slow-down of the progression of T1D) to warrant its further development.

It will involve 72 patients with new-onset T1D. Patients will be randomly (2:1) assigned to receive either ladarixin treatment (400 mg b.i.d. for 3 cycles of 14 days on/14 days off - treatment group) or matched placebo (control group). The two groups will be balanced within centres.

Recruitment will be competitive among the study sites, until the planned number of patients is enrolled. Competitive recruitment has been chosen to increase the speed of recruitment and to account for any difference among study sites in the rate and timing of patient referral. Each site will recruit patients as rapidly as possible up to a maximum of 21 patients (as per randomization list).

Each patient will be involved in the study for a screening period of up to 100 days followed by a post-randomization period up to 52 \pm 2 weeks, as per details below:

- a screening period including 2 or more visits during a period up to 100 days; this includes the time required to confirm the diagnosis;
- a treatment period including 3 treatment cycles of 2 weeks each with 2 weeks interval between cycles and 2 corresponding pre-dose assessment visits;
- 3 follow-up visits scheduled at weeks 13 \pm 1 (month 3), 26 \pm 2 (month 6) and 52 \pm 2 (month 12).

Sample size calculation has been based on the 2-hour area under the curve (AUC) of C-peptide response to a Mixed Meal Tolerance Test (MMTT) observed 12 months after randomization, as these are the only available data that best match the T1D population expected to be randomized in this trial (age, time from diagnosis, etc.) [Lachin, 2011]. On the other hand, the time frame for the primary endpoint (2-hour AUC of C-peptide response to the MMTT) has been set at week 13 \pm 1 in order to maximise the potential to observe an effect of ladarixin, considering the PK profile in humans as well as the reversibility of the pharmacological effect on CXCR1/2 receptors. Such an approach is appropriate for a phase 2 proof of concept trial. Follow-up is anyway extended up to 12 months.

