5.3. ASSIGNMENT OF PATIENT NUMBER

From enrolment (consent signature) to randomization patients will be identified by a Screening number will be assigned in a sequential manner within each site, as patients are enrolled (sign the consent). It will consist of 4 digits, e.g. 0152, where first 2 digits represent site number (01 = site 1), last 2 digits, starting from 50, patient sequential enrolment number within the site (e.g. 50, 51, 52, 53, 54, etc.).

If randomized, the Randomization number will be assigned in a sequential manner within each site, as patients are found to be eligible and are randomized. It will consist of 4 digits, e.g. 0102, where first 2 digits represent site number (01 = site 1), last 2 digits, starting from 01, patient sequential randomization number within the site (e.g. 01, 02, 03, 04, etc.). If a patient is dropped from the study for any reason, the patient's randomization number will not be reassigned.

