9.2. RANDOMIZATION

Patient will be randomized in a 2:1 fashion to either ladarixin or placebo.

The randomization list will be generated with a computer procedure by the method of random permuted blocks in which treatment will be balanced within centres. A master randomization list will be generated, randomizing an excess of patients (a maximum of 21 for each site) to allow competitive recruitment within each centre.

The randomization list will be prepared by an independent statistician and provided to Dompé in a sealed envelope to prevent unblinding. Similarly, the randomization list will be provided to the facility responsible for IMP packaging/labelling for the purpose of IMP preparation.

Individual treatment codes will be provided as a tamper-resistant system (either a sealed envelope or a scratch card) to:

- the Investigator for emergency procedures;
- the Pharmacovigilance for safety procedures.

Individual treatment codes must be kept in a secure location accessible only to designated staff in order to prevent dissemination of the treatment to personnel involved in study conduct who must remain blind.

The randomization code will be broken at study completion, i.e. when the last patient has completed his/her last follow-up visit, and once the database has been locked.

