9.4.2. Analysis of efficacy variables

The 2-hour C-peptide AUC after the MMTT at week 13±1 (primary efficacy endpoint), will be analysed with Student t test for unpaired data using PROC TTEST within SAS[®], including terms for treatment and centre. The estimated treatment difference between ladarixin and placebo will be also presented together with the corresponding 95% confidence interval.

Additional analysis will include the analysis of the AUC at the 3 time points with a single repeated measurements model using PROC MIXED within SAS[®]. The adjusted least squares means will be estimated for each combination of time point and treatment. The treatment effect within each time point will be compared using a two sided test at 0.05 level. The tests of the fixed effects will be presented, together with the estimated least squares means and summary statistics of the raw AUC for each of the two treatments at each time point. The estimated treatment difference between ladarixin and placebo at each time point will be presented together with the corresponding 95% confidence interval. The confidence interval will be generated at a statistical level of 0.05.

The mean in average daily insulin requirements and HbA1c value at the 3 time points will be analysed using a repeated measurements model using PROC MIXED within SAS[®].

The effect of treatment on the cumulative number of severe hypoglycaemic events will be evaluated using an Andersen-Gill analysis with robust sandwich-type variance estimate.

The other secondary efficacy endpoints will be analysed using appropriate parametric and non-parametric tests and appropriate 95% CI will be presented.

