### 4.3. CHANGES TO ANALYSIS FROM PROTOCOL

- 1) Primary analysis of primary efficacy variable has been modified in order to be consistent with the definition of the primary endpoint.

In the study protocol the following analysis was proposed:

“The 2-hour C-peptide AUC after the MMTT at week 13±1 will be analyzed with Student t-test for unpaired data using PROC TTEST within SAS®, including terms for treatment and Centre. The estimated treatment difference between Ladarixin and placebo will be also presented together with the corresponding 95% confidence interval.”

In the present SAP the primary analysis has been modified as follows:

“The 2-hour C-peptide AUC after the MMTT (log(x+1) transformed data) at week 13±1 will be analyzed with Student t-test for unpaired data using PROC TTEST within SAS®, including terms for treatment. The estimated treatment difference between Ladarixin and placebo will be also presented together with the corresponding 95% confidence interval.”.

- 2) The analysis corresponding to the 2-hour AUC C-peptide (log(x+1) transformed data) secondary efficacy endpoint has been reformulated as “The comparisons between groups on 2-hour AUC of C-peptide efficacy endpoint will be carried-out using a mixed linear model with 2-hour AUC of C-peptide as dependent variable, treatment group, visit, treatment by visit interaction as fixed factors of the model and patient as random effect. An unstructured covariance matrix for each patient is considered and the Kenward-Roger adjustment is used for the degrees of freedom”. In the study protocol the following was stated: “Analysis of the 2-hour AUC of C-peptide at the 3 time points (baseline, weeks 26±2 and 52±2) will be performed through a single repeated measurements model using PROC MIXED within SAS®. The adjusted least square means will be estimated for each combination of time point and treatment. The treatment effect within each time point will be compared using a two-sided test at 0.05 level. The tests of the fixed effects will be presented, together with the estimated least squares means and summary statistics of the AUC for each of the two treatments at each time point. The estimated treatment difference between Ladarixin and placebo at each time point will be presented together with the corresponding 95% confidence interval. The confidence interval will be generated at a statistical level of 0.05”.

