### 8.2. MULTICENTRE STUDIES

This study will be conducted by multiple investigators at multiple centers. Site-related differences will not be evaluated and presented in the statistical output as the study does not foresee a randomization stratified by Centre.

---

Document: MEX0114\_SAP\_v4\_4 Final Methods.docx  
Author: [name]

Version Number: Final Version 4.4  
Version Date: [17SEP2019]

Template No: CS\_TP\_BS016 – Revision 4  
Effective Date: 01Apr2016

Reference: CS\_WI\_BS005

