### 16.1.2. PRIMARY ANALYSIS OF PRIMARY EFFICACY VARIABLE

The 2-hour C-peptide AUC after the MMTT at week 13 ± 1 will be transformed as log(x+1) values; transformed AUC will be analyzed with Student t-test for unpaired data using PROC TTEST within SAS® to compare Ladarixin and placebo groups. The estimated treatment difference between Ladarixin and placebo will be also presented together with the corresponding 95% confidence interval.

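### The SAP says randomisation is not stratified by centre when the protocol blocks within centre, and the planned centre term leaves the primary analysis without a valid reason

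*SAP*

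**What the plan says.** **Randomisation.** Protocol 9.2 says the list is "generated with a computer procedure by the method of random permuted blocks in which treatment will be balanced within centres", with up to 21 places for each site. Protocol 5.3 adds that "the Randomization number will be assigned in a sequential manner within each site", the first two digits being the site number. The synopsis states: "The two groups will be balanced within each centre". Protocol 3.1 repeats the balance and ties the 21-patient site cap to the list.

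**Multicentre statement.** SAP 8.2 reads: "Site-related differences will not be evaluated and presented in the statistical output as the study does not foresee a randomization stratified by Centre".

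**Primary analysis.** Protocol 9.4.2 (and the synopsis) plans an unpaired t-test in PROC TTEST "including terms for treatment and centre". SAP 4.3 item 1 prints that text, replaces it with a version containing treatment only, and explains: "Primary analysis of primary efficacy variable has been modified in order to be consistent with the definition of the primary endpoint". SAP 16.1.2 follows: "transformed AUC will be analyzed with Student t-test for unpaired data using PROC TTEST". No model listed in SAP 8.1 contains centre either. SAP 8.4 treats this primary comparison as the only confirmatory one.

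**The concern.** SAP 8.2 rests on a premise that the protocol contradicts in four places. It is also the only statement in the SAP that gives a reason for ignoring centre. A factor used to restrict the randomisation normally belongs in the analysis, and the protocol intended that.

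Within-centre blocking removes most centre-to-centre variation from the treatment difference. A plain t-test still counts that variation in its error term. The standard error is then too large, the test runs below its stated 0.05, and some power is lost. What is at stake is efficiency and a truthful record of the design in the one confirmatory comparison. It is not a false-positive risk.

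**Working it through.** **1. Is the randomisation stratified by centre?**
- Permuted blocks with balance inside each centre: protocol 9.2, synopsis and 3.1.
- A separate run of numbers for each site, up to 21: protocol 5.3 and 9.2. A run of 21 is seven whole blocks of 3, which suits 2:1 allocation.

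Separate blocked sequences per site are stratification by centre, although the protocol does not use that word. The Belgian and German amendments are not among the documents. The SAP cites them for additional assessments at those sites, and nothing suggests that they changed randomisation. SAP 8.2 is therefore wrong.

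**2. Is there a valid reason for dropping centre?** The endpoint definition concerns the variable and the time point. It can explain adding log(x+1) but not removing centre. The reason in SAP 8.2 is false. A true reason exists, namely that an unpaired PROC TTEST cannot carry a centre term, but the SAP does not give it.

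**3. The plan's own sample size.** Inputs: 72 patients, 2:1, one-sided 0.05, 85% power, 24% drop-out (protocol 9.1). The drop-out step is consistent: 54/(1 - 0.24) = 71.05, rounded up to 72, with 36 and 18 evaluable. The power cannot be reproduced, because the SD and control mean are not in the documents. Back-solving gives the implied standardised difference:

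d = (1.645 + 1.036)/√(36 × 18/54) = 2.681/3.464 = 0.774 (0.784 with the exact t distribution).

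**4. Direction and limit of the effect.** Let ICC be the share of variance between centres. With perfect balance within centres, the true variance of the treatment difference is about (1 - ICC) times what the t-test assumes. The large-sample level is P(Z > 1.645/√(1 - ICC)):
- ICC 0.1: P(Z > 1.734) = 0.041
- ICC 0.2: P(Z > 1.839) = 0.033

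Drop-out disturbs the balance, so realistic levels lie between these values and 0.05.

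**5. Simulation.** Assumed, because the documents do not give them: centre layout, block size and ICC. At no more than 21 per site, 72/21 = 3.4, so there are at least 4 centres. Five layouts were used: 4 centres (21, 21, 21, 9), 8 of 9, 10 unequal (21 down to 1), 12 of 6, and 18 of 4. Other settings were blocks of 3, 24% random drop-out (72 × 0.76 = 54.7, so 55 evaluable), effect 0.785 SD, total variance fixed at 1, and 20,000 runs per setting. Simulation error is about ±0.003 on level and ±0.5 points on power.

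| ICC | t-test level | t-test power | Random-centre power (Kenward-Roger) | Gain (points) | Unpooled fixed centres minus t-test (points) |
|---|---|---|---|---|---|
| 0 | 0.048-0.052 | 85.1-85.7% | 85.3-86.0% | no loss | -0.5 to -6.1 |
| 0.1 | 0.043-0.048 | 86.1-87.0% | 87.4-88.4% | 1.3-1.6 | +1.1 to -2.9 |
| 0.2 | 0.038-0.042 | 87.0-87.9% | 89.5-91.0% | 2.5-3.1 | +3.0 to -0.4 |

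The level of the random-centre test was 0.048-0.054 throughout. The worst case for fixed effects was always 18 centres of 4. Blocks of 6, rerun for two layouts, gave the same pattern.

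**6. Cross-checks.** A separately programmed simulation (6 or 10 centres of random size, blocks of 3 or 6, effect 0.774) gave a t-test level of 0.037-0.041 at ICC 0.2, against 0.048-0.051 with fixed centres. At ICC 0, fixed centres cost about 1-3 points. A smaller run of the random-centre model with simpler degrees of freedom (2,500 runs per setting; power error 1.3-1.4 points) showed no loss at ICC 0. Its gains were 1.0-1.5 points at ICC 0.1 and 3.0-3.9 at ICC 0.2.

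**The case against.** **The change is disclosed.** SAP 4.3 prints the protocol text and its replacement together, and SAP 5.3 places SAP authorisation and database lock ahead of unblinding. This stands: the change is poorly explained, not hidden.

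**The protocol analysis could not be run.** Either the named test or the centre term had to go, and the SAP kept the test. This also stands, and it would have been a legitimate reason to revise. The SAP does not state it, and dropping the randomisation factor was not the only way out.

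**SAP 8.2 concerns site outputs and does not mention the primary test.** Correct. The link is only that 8.2 holds the SAP's sole centre-specific reason.

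**The effect is small and conservative.** The t-test keeps the planned 85% power in every main-simulation scenario. C-peptide is assayed centrally and the meal test is standardised, so the ICC may be low. This stands and limits the weight of the point.

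**The random-centre model may be fragile.** Its level reached 0.054 in one setting, just beyond simulation error. The centre variance was estimated as zero in 53-63% of runs at ICC 0 and in 9-14% at ICC 0.2. A zero estimate simply returns the unadjusted comparison, so nothing is lost, but the SAP should say so in advance.

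**Conclusion.** The concern holds. SAP 8.2 is wrong as written, and the centre term was removed from the confirmatory analysis for a reason that does not address centre.

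The statistical consequence is modest: no bias, no false-positive inflation, and a test that is conservative if centres differ. A random centre effect would gain about 1.3-1.6 points of power at ICC 0.1 and 2.5-3.1 at ICC 0.2, and would lose none at ICC 0. These sizes depend on assumed centre layouts, ICCs and random drop-out. The textual contradiction depends on no assumption. The wording corrections are needed whatever the ICC. The model change is a low-cost improvement that brings the analysis back to the design and to the protocol's intent.

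**What to change.** 1. **SAP 8.2:** state that randomisation is in permuted blocks within centre.
2. **SAP 4.3 item 1:** give a reason that addresses centre, for example that PROC TTEST cannot carry the planned term.
3. **SAP 16.1.2, before unblinding:** analyse log(x+1) week-13 AUC in PROC MIXED with treatment fixed, centre as a random intercept and Kenward-Roger degrees of freedom (already used in SAP 16.2.2). Keep the one-sided 0.05 test and the 95% confidence interval. State that a zero centre-variance estimate is accepted as the unadjusted comparison, and name a fallback for non-convergence.
4. **Avoid unpooled fixed effects for small sites.** If fixed effects are preferred, pool small centres by a size rule fixed at the blind data review.
5. **Keep the unadjusted t-test** as a sensitivity analysis. Adding centre to the secondary mixed models is optional.

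The cost is some SAP wording and one procedure change. The drawback is that the centre variance is estimated from few centres. In the main simulations the level nevertheless stayed at 0.048-0.054, with no power lost when centres did not differ. Unpooled fixed effects would cost about 0.5 to 6 points in that case.

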### 8.3. MISSING DATA

If the actual time for Mixed Meal Tolerance Test is not recorded, the scheduled time will be used.

Missing C-peptide values will be imputed with the average of the C-peptide value that precedes and follows the missing value. Missing data in C-peptide at 180 minutes (final) will be replaced by the last non-missing value.

The last available basal sample time will be used as the first sample time in the computation of the AUC, and the average of the basal sample values (Basal #1 and Basal #2) will be used as the first sample value in the computation of the AUC.

Other missing data will not be replaced.

The number of patients with missing data will be presented under the “*unknown*” category. Missing values will be included in the denominator count when computing percentages.

When continuous data will be summarized, only the non-missing values will be evaluated for computing summary statistics.

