9.4. STATISTICAL METHODOLOGY

All patient data collected on the CRF and on the Diary Card will be listed by patient and centre.

Appropriate descriptive statistics will be produced, according to the variable. For continuous data the

mean, standard deviation, standard error of the mean, median and range (minimum and maximum) and lower and upper 95% confidence limits (CI) will be presented. For categorical data, frequencies and percentages will be presented. If appropriate, confidence intervals around the mean or the proportions will be presented.

All the AUC analyses will be based on actual rather than scheduled timings and will be calculated using the trapezoidal rule. If the actual time is not recorded, the scheduled time will be used instead. When C-peptide values are below the limit of detection (0.2 ng/mL), a value of 0.2 ng/mL will be assumed in the calculation of area under the curve. Missing C-peptide values will be imputed via linear interpolation, and the last available basal sample (time and value) will be used as the first sample in the computation of the AUC. Inferential statistics will be conducted on $\log(x+1)$ transformed data, according to Lachin [2011].

Unless otherwise specified, the significance level used for statistical testing will be 0.05 and one-sided tests will be used.

Besides statistical analysis presented below, additional post-hoc analysis may be produced to further allow comparison between ladarixin and placebo, according to the results obtained. They may include change from baseline in C-peptide AUC, peak stimulated C-peptide, time to peak, etc.

A Statistical Analysis Plan will be issued describing details of all the statistical methods and analysis to be applied to trial results. Any change in the planned analysis will be documented. The data will be presented in the clinical study report.

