14.4.2. Mixed Meal Tolerance Test

The MMTT will be performed after an overnight fast, according to [Greenbaum \(2008\)](#) at baseline (within 1 week prior of randomization) and at each follow-up visit on weeks 13_±1, 26_±2 and 52_±2. Screening MMTT should not be performed within one week of resolution of a diabetic ketoacidosis event, defined as the presence of hyperglycemia (blood glucose >200 mg/dL); pH <7.3 or HCO₃ <15; ketones positive in the serum or urine.

Prior to the test, patients will withhold long-acting insulin on the morning of the test. Rapid-acting and short-acting insulin will be allowed up to 6hrs and 2 hrs, respectively, before the test. Test will be re-scheduled if the patient has a capillary glucose value of >200mg/dL or <70mg/dL.

The test will be initiated before 10 a.m. After 2 pre-meal basal samples have been drawn between -20 to 0 min (basal 1 and basal 2), patients will be given 6mL/kg of Boost[®] High Protein Nutritional Drink (Nestlé Nutrition) up to a maximum of 360mL, to be drunk within 5 min. Post-meal samples will be drawn at 15_±5, 30_±5, 60_±10, 90_±10, 120_±15, 180_±15 min after the meal.

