  - Proportion of patients maintaining a residual  $\beta$ -cell function [Time points: weeks 13 $\pm$ 1, 26 $\pm$ 2 and 52 $\pm$ 2].
  - C-peptide AUC (15-120 min) above fasting value [Time points: baseline, weeks 13 $\pm$ 1, 26 $\pm$ 2 and 52 $\pm$ 2].
  - Percent change from baseline of 2-hour AUC of C-peptide response to the MMTT [Time points: weeks 13 $\pm$ 1, 26 $\pm$ 2 and 52 $\pm$ 2].
  - Proportion of patients with HbA1c < 7% and absence of episodes of severe hypoglycemia from the previous visit [Time points: weeks 13 $\pm$ 1, 26 $\pm$ 2 and 52 $\pm$ 2].
  - Proportion of responders at week 52, defined as patients with percent decrease from baseline in 2-hour AUC of C-peptide above the median percent decrease from baseline to Week 52.
- 7) Planned subgroups descriptive analyses on the efficacy endpoints according to age class at Screening ( $\leq$  25 and > 25 years) and to fasting C-peptide (Pre-MMTT) ( $\leq$  median value and > median value) at Screening visit.
- 8) A subgroup analysis on 2-hour AUC of C-peptide response to the MMTT stratified by the number of positivity in auto-antibodies (1, 2, 3, and 4) at Screening visit has been planned.
- 9) The approach to deal missing C-peptide values has been changed: the sentence “missing C-peptide values will be imputed via linear interpolation” of the study protocol has been changed in “Missing C-peptide values will be imputed with the average of the C-peptide value that precedes and follows the missing value. Missing data in C-peptide at 180 minutes (final) will be replaced by the last non-missing value.”.
- 10) In the study protocol was stated “When C-peptide values are below the limit of detection (0.2 ng/mL), a value of 0.2 ng/mL will be assumed in the calculation of area under the curve.” This rule to address the C-peptide values below 0.2 ng/mL will not be applied. C-peptide values will analysed as reported in the CRF.

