## 7.2. STUDY BASELINE

Unless otherwise specified, study baseline is defined as the last non-missing measurement taken prior to IMP administration (including unscheduled assessments). In the analysis of MMTT variables (Glucose, C-peptide and Glucagon) (reported and calculated parameters) the Basal of those variables is defined as the average of the two basal values (Basal #1 and Basal #2 (pre-meal values)). If one of the two basal values is missing the non-missing basal value will be considered as Basal in the analysis of MMTT variables.

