 Furthermore, the 2-hour AUC of C-peptide response calculation will be based on actual rather than scheduled timings and will be calculated using the trapezoidal rule. If the actual time is not recorded, the scheduled time will be used instead. Missing C-peptide values will be imputed with the average of the C-peptide value that precedes and follows the missing value. Missing data in C-peptide at 180 minutes (final) will be replaced by the last non-missing value, and the last available basal sample (time and value) will be used as the first sample in the computation of the AUC.

Document: MEX0114\_SAP\_v4\_4 Final Methods.docx  
 Author: [name]

Version Number:  
 Version Date:

Final Version 4.4  
 [17SEP2019]

Template No: CS\_TP\_BS016 – Revision 4  
 Effective Date: 01Apr2016

Reference: CS\_WI\_BS005

- Baseline MicroRNA-375 expression level (Copies/mL)
- T-cells response (T-cell proliferation (CD4) and rate of precursor (CD8)).
- Renal Reserve: Creatinine Clearance (CLcr) (mL/min) – calculated in the CRF. The formula that will be used to verify the calculation is reported in section 11.1.
- Time since first insulin injection (days) – calculated as specified in section 11.1.

Default frequency tabulations will be provided for categorical variables and descriptive summary statistics will be provided for continuous parameters.

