## 16. ANALYSIS OF EFFICACY AND SAFETY VARIABLES

All the efficacy analyses will be performed for the ITT set.

All the AUC analyses (2-hour and 15-120) will be based on actual rather than scheduled timings and will be calculated using the trapezoidal rule. If the actual time is not recorded, the scheduled time will be used instead.

C-peptide AUC values will be transformed to the  $\log(x+1)$  [selected by TrialNet as the appropriate transformation for MMTT C-peptide AUC].

C-peptide 2-hour AUC values will be calculated from 0-120 C-peptide values of the MMTT. C-peptide (15-120) above fasting AUC will be calculated on the changes from Basal in C-peptide values of the MMTT. Basal value is the average

Document: MEX0114\_SAP\_v4\_4 Final Methods.docx

Author: [name]

Version Number:

Final Version 4.4

Version Date:

[17SEP2019]

Template No: CS\_TP\_BS016 – Revision 4

Reference: CS\_WI\_BS005

Effective Date: 01Apr2016

Copyright © 2009, 2010, 2012, 2016 Quintiles Transnational Corp. All rights reserved.

The contents of this document are confidential and proprietary to Quintiles Transnational Corp. Unauthorized use, disclosure or reproduction is strictly prohibited.

of Basal #1 and Basal #2 C-peptide values in MMTT. The last non-missing time of Basal #1 and Basal #2 values will be used to calculate the time differences in the AUC.

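### The SAP imputes missing C-peptide samples by an unweighted mean although sampling is uneven, and it gives two different starting values for the baseline AUC (minor)

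*SAP*

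**What the plan says.** **Imputation.** Protocol 9.4: "Missing C-peptide values will be imputed via linear interpolation". SAP 8.3: "Missing C-peptide values will be imputed with the average of the C-peptide value that precedes and follows the missing value". SAP section 11 repeats the SAP rule, and 4.3 item 9 declares the change without giving a reason.

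**Timing.** Protocol Appendix 14.4.2: "Post-meal samples will be drawn at 15_±5, 30_±5, 60_±10, 90_±10, 120_±15, 180_±15 min after the meal". SAP section 16: "All the AUC analyses (2-hour and 15-120) will be based on actual rather than scheduled timings", by the trapezoidal rule.

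**First sample of the AUC.** In its baseline MMTT entry, SAP section 11 says "the last available basal sample (time and value) will be used as the first sample in the computation of the AUC", as the protocol does. SAP 8.3 says "the average of the basal sample values (Basal #1 and Basal #2) will be used as the first sample value", placed at the last basal time. Section 7.2 agrees with 8.3 ("the Basal of those variables is defined as the average of the two basal values (Basal #1 and Basal #2 (pre-meal values"), and so does section 16. The list of changes in 4.3 does not mention the move from the last basal value to the mean.

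**Values below the limit.** The protocol set them to 0.2 ng/mL. SAP 4.3 item 10: "This rule to address the C-peptide values below 0.2 ng/mL will not be applied". Item 10 goes on to say that values are analysed as the CRF has them.

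**The concern.** A plain mean equals linear interpolation only when the missing sample lies midway between its neighbours. The MMTT schedule is not evenly spaced, and the windows allow further drift. The SAP therefore integrates on actual times but fills gaps as if time did not matter.

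The two starting values are a direct contradiction for the baseline AUC. That AUC is the denominator of percent change, the covariate in its model (SAP 8.1 and 16.2.2 item 2), and an input to the week-52 responder endpoint (16.3.1 item 6). The responder endpoint is cut at a median, so a small shift can reclassify a patient close to it.

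At stake is a derivation that two programmers could code differently and that departs from the protocol in one respect without saying so. The size of any bias is a secondary matter.

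**Working it through.** The plan gives no figure for the effect of these rules, so there is none to reproduce. The sample-size statement does not enter.

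**1. Weights at scheduled times (0, 15, 30, 60, 90, 120, 180 min).** The linear weight of the later neighbour is (t − t_before)/(t_after − t_before).

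- 15 min (basal at 0): 15/30 = 1/2. 60 min: 30/60 = 1/2. 90 min: 30/60 = 1/2. The two rules are identical.
- 30 min: (30 − 15)/(60 − 15) = 1/3.
- 120 min: (120 − 90)/(180 − 90) = 1/3.

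**2. Shift, averaging minus linear.** In the value it is (1/2 − 1/3) = 1/6 of the difference between the neighbours. In the trapezoid over 0 to 120 min, the 30-min sample has weight (60 − 15)/2 = 22.5 and the 120-min sample (120 − 90)/2 = 15.

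- 30 min: 22.5/6 × (C60 − C15) = 3.75 × (C60 − C15)
- 120 min: 15/6 × (C180 − C90) = 2.5 × (C180 − C90)

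**3. Size under four assumed profiles.** The documents give none. Values are in nmol/L at 0/15/30/60/90/120/180 min:

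- A: .25/.30/.45/.60/.60/.55/.45
- B: .30/.40/.60/.90/.95/.85/.60
- C: .40/.60/1.0/1.5/1.5/1.2/.70
- D: .20/.25/.50/1.0/1.2/1.0/.40

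| Profile | 30 min: shift / linear AUC | 120 min: shift / linear AUC |
|---|---|---|
| A | 1.125 / 59.625 = +1.9% | −0.375 / 60.75 = −0.6% |
| B | 1.875 / 89.25 = +2.1% | −0.875 / 89.75 = −1.0% |
| C | 3.375 / 140.25 = +2.4% | −2.0 / 143 = −1.4% |
| D | 2.8125 / 97.5 = +2.9% | −2.0 / 96.5 = −2.1% |

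**4. Which rule is closer to the AUC with the sample observed?** Errors are linear versus averaging, profiles A to D.

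- 30 min: −1.85% vs 0.0%; −0.83% vs +1.25%; −1.58% vs +0.79%; 0.0% vs +2.88%. Averaging is closer in two of the four.
- 120 min: 0.0% vs −0.62%; −0.28% vs −1.25%; +0.35% vs −1.05%; −1.03% vs −3.08%. Averaging is further away in all four.

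**5. Actual times.** Within the windows, the linear weight on the 180-min value for a missing 120-min sample runs from (105 − 100)/(195 − 100) = 0.05 to (135 − 80)/(165 − 80) = 0.65, against a fixed 0.5. If the sample was never drawn and 120 min is used as its time, the range is 20/95 = 0.21 to 40/85 = 0.47.

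**6. Effect on the primary scale.** Taking the AUC as a mean in nmol/L (an assumption; the documents do not fix the unit), the largest shift in log(AUC + 1) is 0.013 per affected patient. If 10% of an arm were affected (also assumed), the arm mean would move by about 0.10 × 0.013 = 0.001. For an assumed control mean of 0.3 to 0.6 nmol/L, a 50% difference is ln(1.45/1.30) = 0.11 to ln(1.90/1.60) = 0.17.

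**7. First sample.** If the two basals differ by d, the last value and the mean differ by d/2. The first sample has weight (15 − t0)/2, which is 7.5 at 0 min and 17.5 at −20 min. The AUC therefore moves by 3.75d to 8.75d. With d = 0.1 nmol/L and profile A (the smallest AUC), that is 0.375/60.75 = 0.6% at 0 min and 0.875/60.75 = 1.4% at −20 min. The second figure is a bound: the definitions differ only when both basals are present, and the later of the two will normally be drawn after −20 min.

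**The case against.** The defence is substantial. The imputation change is declared. On schedule it makes no difference at 60 or 90 min, nor at 15 min with the basal at 0. A reader might infer that averaging is uniformly worse, or a systematic error that interpolation avoids. The assumed profiles do not support that: at 30 min averaging was nearer the full-data AUC in two of four. What stands is that a time-blind rule does not fit an AUC integrated on actual times, and that no reason is given for leaving the protocol's rule.

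A reader might also infer that the primary variable itself has two conflicting definitions. It does not. The stray clause sits in the baseline MMTT entry of section 11. The primary test (SAP 16.1.2) is an unadjusted t-test on week-13 AUC with no baseline term, and for that visit 8.3 and section 16 agree on the mean basal. The gap between last and mean basal also has no stated direction, so at baseline it acts as noise.

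Finally, a reader might infer that the SAP has no rule below detection, so that undetectable profiles are averaged upwards or lost, mainly on placebo. Item 10 does give a rule. Nothing in the documents says that the CRF holds non-numeric entries or that they would be read as missing; assay methods are left to the Laboratory Manual (Protocol Appendix 14.4.1). What remains is narrow: item 10 names no number for a result reported only as below the limit.

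**Conclusion.** Two defects stand, both minor. The unweighted mean departs from linear interpolation at 30 and 120 min on schedule, and at other times when actual times drift. At scheduled times its effect is about 1 to 3% of AUC in affected patients under the assumed profiles, by the same rule in both arms. It is not shown to alter the primary conclusion. The baseline AUC has two incompatible starting values, worth typically under 1% of AUC. That touches percent change, its covariate and the responder endpoint, but not the week-13 comparison. The move to the mean basal is also missing from 4.3, which is a reporting gap at every visit.

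The algebra is exact. The percentages rest on illustrative profiles, and the rate of missing samples is unknown. The below-limit point is conditional and has no effect if the laboratory supplies numeric values.

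**What to change.** - In SAP 4.3, 8.3 and 11, restore linear interpolation, computed on actual sample times.
- In section 11, delete the clause that starts the AUC from the last basal time and value, so that 8.3 governs every visit. List the change from last basal value to mean basal in 4.3.
- In 4.3 item 10, state that a result reported only as below the limit takes the protocol's 0.2 ng/mL and is not treated as missing.

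The cost is a few sentences of SAP text and a few lines of derivation code. No new data are needed and the primary test is unchanged.
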